3.2 Randomization and blinding

3.2.1 Randomization

A randomization schedule will be computer-generated before the start of the study. After all screening procedures are performed and results of screening tests are available (i.e., between the Screening visit and [REDACTED]), [REDACTED] will be activated in the interactive voice recognition system (IVRS), and assigned randomly on a [REDACTED] basis to the following treatment groups for cohorts of [REDACTED], respectively:

- A: [REDACTED] tildrakizumab, [REDACTED]
- B: Placebo, administered by [REDACTED]
[REDACTED]

Randomization will be performed by the [REDACTED]. Subjects will be stratified by prior anti-tumor-necrosis factor (anti-TNF) use (yes/no). Subjects with prior anti-TNF use will be capped [REDACTED] [REDACTED] of the total number of subjects.

Statistical Analysis Plan (SAP)

[REDACTED] (Stage 1) subjects will begin upon study approval; recruitment for [REDACTED] (Stage 2) subjects will begin only upon written notification by the Sponsor to the Competent Authorities and Investigators.

3.2.2 Blinding

This is a double-blind study. None of the study team, the subject, and the Sponsor (or representative) will be aware of the administered study drug to each subject until the completion of their double-blind treatment ([REDACTED] visit) and wash-out period. A separate document will provide further details related to unblinding of personnel involved in reporting activities for the Interim Analysis (IA).

PK and anti-drug antibodies (ADA) data will be kept confidential only after database lock and unblinding at study completion.

3.2.3 Unblinding

In an emergency, in which the Investigator must know a subject's treatment allocation to ensure the subject's safety, the Investigator will contact IVRS. When the Investigator contacts the system to break a treatment code for a subject, he/she must provide the requested subject identifying information and confirm the necessity to break the treatment code for the subject. The Investigator will then receive details of the IMP for the specified subject. The system will automatically inform the ICON Site Monitor, the medical monitor, and the [REDACTED] Project Manager that the code has been broken, but no treatment assignment will be communicated.

3.3 Study treatments and assessments

The maximum study duration from screening to end of the wash-out period is [REDACTED].

All subjects eligible for study participation will enter the double blind treatment period and receive one of the 2 treatments assigned per the schedule outlined in the study flow chart. Study drug will be supplied as pre-filled syringes and a subject at a visit is expected to receive two syringes packed in a kit. Below are the details:

[figure not shown]
- [REDACTED] [REDACTED]: subjects will receive tildrakizumab [REDACTED] ([REDACTED] of [REDACTED]) at [REDACTED].
- Placebo arm, [REDACTED] will be administered at [REDACTED] and [REDACTED]. Subjects will then receive tildrakizumab [REDACTED] at [REDACTED].

If a subject misses a visit and/or a scheduled dose of IMP, the site must reschedule a visit to ensure the dose of IMP is taken as soon as possible within the visit window. If after 2 attempts to reschedule, the subject still is not able to take the dose, the Sponsor should be contacted to

Statistical Analysis Plan (SAP)

[figure not shown]
determine if the subject should be discontinued from the study.

[figure not shown]
A detailed description of procedures and assessments to be conducted during this study is summarized in the Schedule of Assessments in [REDACTED] below.

[figure not shown]
Statistical Analysis Plan (SAP)

[figure not shown]
Table 2: Schedule of Assessments (Part 1 and 2)

[figure not shown]

[figure not shown]
Statistical Analysis Plan (SAP)

[figure not shown]

Statistical Analysis Plan (SAP)

[figure not shown]

[figure not shown]
Statistical Analysis Plan (SAP)

[Redacted content]

[Redacted content]

[figure not shown]

Statistical Analysis Plan (SAP)

I

Statistical Analysis Plan (SAP)

Table 2: Schedule of Assessments (Part 3)

Statistical Analysis Plan (SAP)

[Redacted content]

Statistical Analysis Plan (SAP)

4 STUDY ENDPOINTS

4.1 Primary efficacy endpoint

The primary efficacy endpoint is the proportion of subjects who achieve ASAS20 at [REDACTED]

ASAS20 response is defined as an improvement of [REDACTED]

[REDACTED]
[REDACTED]
[REDACTED]
[REDACTED]
[REDACTED]
[REDACTED]

The components of the ASAS [REDACTED] assessments that will be used in this study are:

- PtGA of disease activity (VAS in mm)
- Total Back Pain (VAS in mm)
- BASFI (VAS in mm)
- Inflammation [average score of questions 5 and 6 of BASDAI] (VAS in mm)

For the details on BASFI derivation, see [REDACTED] for the related endpoint. For inflammation, if either [REDACTED] of BASDAI is missing, non-missing score will be used. If both [REDACTED] are missing, then Inflammation is set to missing.

For any component which is not on a scale of [REDACTED], they will be converted to 0 to 100 before calculating ASAS.

If the value in any of the components at a time point is missing, the component variables that are not missing will be used to determine the response status. As a general principle, if there are sufficient non-missing components to determine whether the ASAS endpoint is a response or non-response, then ASAS endpoint is not missing, else if the available non-missing components are not sufficient to determine the response status of ASAS endpoint then it is considered missing.

If the baseline value of any component is [REDACTED] the following algorithm will be used in evaluating the percent change from baseline:

- If change from baseline is also equal to 0, then percent change from baseline is set to be [REDACTED];
- If change from baseline is [REDACTED] then percent change from baseline is set to be [REDACTED]

These percentages will be used to derive the ASAS endpoints.

4.2 Secondary efficacy endpoints (up to [REDACTED])

The secondary efficacy endpoints of this study are:

Statistical Analysis Plan (SAP)

Parts 1 and 2

- The proportion of subjects who achieve ASAS20 at [REDACTED]
- The proportion of subjects who achieve ASAS40 at [REDACTED]

- The proportion of subjects who require adjustment of background therapy

4.3 Exploratory endpoints

The exploratory endpoints of this study are:

Parts 1 and 2:

- The proportion of subjects who achieve ASAS20 or ASAS40 at other measured time points
- The proportion of subjects who achieve ASAS70 at measured time points

ASAS70 will be derived similarly as for ASAS40 by using [REDACTED] and [REDACTED]. i.e. ASAS70 response is defined as an improvement of [REDACTED] absolute improvement of [REDACTED] units from Baseline in a VAS for at [REDACTED] domains: PtGA; Total Back Pain; BASFI; and Inflammation. No worsening of [REDACTED] VAS on a [REDACTED] scale in the remaining [REDACTED] domain.

- The proportion of subjects who achieve a ASAS5/6 response at measured time points

ASAS5/6 response is defined as a [REDACTED] s (physical function [BASFI], Total Back Pain, PtGA of disease activity, Inflammation [mean of [REDACTED] of the BASDAI], spinal mobility [BASMI], and acute phase reactants [CRP]).

- Change from Baseline in ASAS components at measured time points
- Change from Baseline in BASDAI at measured time points

BASDAI is derived by computing the mean score of the [REDACTED] and then adding that value to the sum of the score for the [REDACTED] and then [REDACTED]. It may be written as:

$$\text{BASDAI} = \frac{\text{PtGA} + \text{Total Back Pain} + \text{BASFI} + \text{Inflammation}}{4}$$

In the case of any single missing question, the BASDAI will be calculated using the remaining [REDACTED] [REDACTED]. Specifically, if [REDACTED] [REDACTED] [REDACTED] [REDACTED] is missing,

Statistical Analysis Plan (SAP)

[REDACTED]
[REDACTED]
[REDACTED] If more [REDACTED].

BASDAI score ranges from [REDACTED].

- Change from Baseline in BASMI at measured time points

BASMI is a combined index to assess spinal mobility. BASMI score is collected on the CRF page and ranges [REDACTED].

- Change from Baseline in BASFI at measured time points

BASFI is derived by computing the mean of the score for the 10 questions. BASFI can be calculated with up to 3 missing items by adjusting the denominator for the number of non-missing items. If more than 3 items are missing, BASFI should be set to missing.

- Change from Baseline in ASQoL at measured time points

ASQoL total score is calculated by summing the [REDACTED] and ranges [REDACTED]. Cases with more than three missing items (ie more than [REDACTED]) cannot be allocated a total score. For cases with between one and three missing items, the total score is calculated as follows: [REDACTED] for the items affirmed and [REDACTED]

- Change from Baseline in VAS (total back pain and nocturnal pain score) at measured time points

- Change from Baseline in ASDAS-CRP and ASDAS-ESR at measured time points

[REDACTED]
[REDACTED]
[REDACTED]
[REDACTED]
[REDACTED]

Note: Back Pain is from BASDAI [REDACTED]; Duration of Morning Stiffness is from BASDAI [REDACTED]; Peripheral Pain/Swelling is from BASDAI [REDACTED]; Patient Global is from PtGA of disease activity [REDACTED]; CRP - the natural logarithm of CRP in mg/L; ESR- the square root of ESR in mm/h.

- Change from Baseline in MASES at measured time points

MASES score is recorded in the CRF and ranges [REDACTED].

- Change from Baseline in SF-36 at measured time points [REDACTED]

Statistical Analysis Plan (SAP)

- Change from Baseline in FACIT-fatigue at measured time points

FACIT-fatigue is a [] item questionnaire with each item score ranges from [] FACIT-fatigue total score ([]) is calculated by summing the [] items with [] being reversed [] prior to summing.

In case of some answers are missing, the total score is prorated from the score of the answered items as long as more than 50% of the items are answered. ie, $\text{FACIT-fatigue} = 13 * \text{mean}(\text{non-missing of Q1 to Q13})$.

- Change from Baseline in TJC46 and SJC44 at measured time points
- Change from Baseline in hsCRP serum levels at measured time points
- Change From Baseline in SPARCC MRI Index of Disease Activity Score of the SI Joints at measured time points
- Change From Baseline in SPARCC MRI Index of Disease Activity Score of the Spine at measured time points
- Change From Baseline in Modified Berlin ASspiMRI at measured time points

Part 3:

ASAS20, ASAS40, ASAS70, ASAS5/6, ASAS components, BASDAI, BASMI, BASFI, SF-36, VAS (total back pain and nocturnal pain score), MASES, FACIT-fatigue, TJC46, and SJC44 at measured time points.

4.4 Safety endpoints

The safety endpoints of this study are:

- Adverse events (AEs)
- Laboratory assessments
- Suicidal ideation and behavior (C-SSRS)
- Vital signs
- ECG
- Physical examination
- ADA to tildrakizumab, including titer and neutralizing antibodies

Statistical Analysis Plan (SAP)

5 SAMPLE SIZE AND POWER

In each subject cohort (AS and nr-axSpA), approximately 45 subjects will be randomized per arm in a 1:1 ratio to tildrakizumab 200 mg or placebo and will be stratified by anti-TNF use (yes/no). This sample size achieves 80% power (accounting for futility assessment) to detect a treatment effect in ASAS20 at [REDACTED] (placebo ASAS20 = [REDACTED]; tildrakizumab ASAS20 = [REDACTED]). The test statistic used is the [REDACTED] Cochran-Mantel-Haenszel (CMH) test at the [REDACTED] significance level. A [REDACTED] drop-out rate has been assumed.

Statistical Analysis Plan (SAP)

6 ANALYSIS POPULATIONS

6.1 Full Analysis Set (FAS)

The FAS will include all randomized subjects who have received at least 1 dose of IMP (tildrakizumab or placebo). Analyses will be based on randomized treatment.

6.2 Per Protocol Analysis Set (PPAS)

The PPAS will include all subjects in the FAS without any major protocol deviations that could have influenced the validity of the data for the primary efficacy variables. The deviations may include but are not limited to:

- Key inclusion/exclusion criteria not satisfied
- Presence of relevant protocol deviations with respect to factors likely to affect the efficacy of treatment where the nature of protocol deviation will be defined before breaking the blind
- Rescue medication use
- Inadequate study medication compliance which will be determined before breaking the blind

Major protocol deviations to be excluded from the PPAS will be finalized and documented in a memo prior to the lock and unblinding of the database.

6.3 Safety Analysis Set

The Safety Analysis Set will include all randomized subjects who received at least 1 dose of IMP. Analyses will be based on the actual treatment received.

6.4 PK Analysis Set

The PK Analysis Set will include all subjects in the Safety Analysis Set who have sufficient tildrakizumab concentration data to obtain reliable estimates of at least one PK parameters.

6.5 ADA Evaluable Set

The ADA Evaluable Set will include all subjects in the Safety Analysis Set who have at least 1 ADA data point after the date of first IMP administration. Assay results from the placebo portion of the trial will not be included in the immunogenicity assessment, although subjects who are randomized to placebo in Part 1 will be included in the assessment if they are treated with tildrakizumab in Part 2.

6.6 Protocol deviations/violations and exclusions from analysis sets

All deviations and exclusions of subjects from analysis sets will be identified at the Classification

Statistical Analysis Plan (SAP)

Meeting just prior to study unblinding, through clinical review input provided by Sponsor, using the following sources of information:

- Supportive subject listings, provided by the ██████ lead statistician ahead of the Classification Meeting, based on data recorded on the eCRF.
- Protocol Deviation Logs, provided by ██████ Medical/Clinical.

Further, deviations from the protocol will be classified as major/minor or key/non-key depending on documentation in ██████

The protocol deviations that will lead to subject exclusion from the PPAS are listed as below. It is possible that unexpected deviations will arise as the study moves forward. Therefore, more deviations may be added to the list later. Prior to database lock, a classification meeting will be conducted to identify subjects to be excluded from PPAS, and the decision will be documented in a separate file.

- Subject with BASDAI ██████ at Screening or Response to the BASDAI question 'How would you describe the overall level of AS neck, back or hip pain you have had?' of ██████ on the VAS ██████ at Screening
- Non-compliance with study treatment ██████)
- Disallowed concomitant medications
- Treatment error - at least one dose of randomized treatment and one dose of incorrect treatment were administered to a subject.

Statistical Analysis Plan (SAP)

7 STATISTICAL CONSIDERATIONS AND ANALYSIS

7.1 Derived Variables

Details for deriving efficacy variables are discussed in [REDACTED]. The below set of variables are the basic demographic variables and some general variables.

Variables	Formula
Body mass index (BMI; kg/m ²)	weight (kg)/[height (m)] ²
Study day at any visit	(visit date – date of first IMP administration) + 1 for visit dates on or after first IMP dosing date; (visit date – date of first IMP administration) for visit dates before first IMP dosing date
Change from baseline	[REDACTED]
Percent change from baseline	[REDACTED]

7.2 Handling of missing data and outliers

7.2.1 Missing data analysis methods

In the primary analysis, ASAS20 response rate at [REDACTED], missing values will be handled by setting the ASAS20 value to nonresponsive. This approach will be used for all “response-type” endpoints (ASAS40, ASAS70, and ASAS5/6) at all time points.

For a composite “response-type” endpoint (such as ASAS[REDACTED]), if values in any of the components at a time point are missing, the component variables that are not missing will be used to determine the response status. If one cannot determine the response status in the presence of missing components, then the composite response-type endpoint status is considered “non-response” for that time point.

For the BASDAI, BASMI, BASFI, MASES, SF-36, and FACIT instruments, rules suggested by the developers of these will be followed in calculating scores when individual question/items may be missing.

Details on handling missing data are outlined in [REDACTED].

In general, missing values in any of the endpoints will not be imputed when summarizing these endpoints using descriptive statistics.

In addition, missing values for safety endpoints will not be imputed.

7.2.2 Handling of missing or incomplete dates

Imputation rules for missing or partial AE start date are defined below:

Statistical Analysis Plan (SAP)

If the start date has month and year but day is missing, the first day of the month will be imputed

- If this date is earlier than the first dose date, then the first dose date will be used instead.
- If this date is later than the stop date (possibly imputed), then the stop date will be used instead.

If the start date has year, but day and month are missing, the 1st of January will be imputed

- If this date is earlier than the first dose date, then the first dose date will be used instead.
- If this date is later than the stop date (possibly imputed), then the stop date will be used instead.

If the start date of an event is completely missing, then it is imputed with the first dose date.

Imputation rules for missing or partial AE stop date are defined below:

- If the stop date has month and year but day is missing, the last day of the month will be imputed
- If the stop date has year, but day and month are missing, the 31th of December will be imputed

After the imputation, the imputed dates will be compared against the date of death, if available. If the date is later than the date of death, the date of death will be used as the imputed date instead.

Imputation rules for missing or partial medication start/stop dates are defined below:

Missing or partial medication start date:

- If only Day is missing, use the first day of the month.
- If Day and Month are both missing, use the first day of the year.

Missing or partial medication stop date:

- If only Day is missing, use the last day of the month.
- If Day and Month are both missing, use the last day of the year.
- If Day, Month and year are all missing, assign ‘continuing’ status to stop date

Statistical Analysis Plan (SAP)

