##### 12.1.1.1 Adverse Event/Reaction

An AE is defined as “any untoward medical occurrence in a subject, or clinical investigation subject administered a pharmaceutical product, and which does not necessarily have a causal relationship with this treatment. An AE can therefore be any unfavorable and unintended sign, symptom or disease temporally associated with the use of a medicinal (investigation) product, whether or not related to the medicinal (investigational) product”.

Any relevant observations made at the [REDACTED]

[REDACTED] are to be recorded on the AE eCRF, but will not be considered treatment-emergent AEs (TEAEs) and will be reported separately from TEAEs. Any relevant observations following the first dose of IMP will be recorded as an AE in the subject's AE eCRF; this includes physical examination findings, clinically relevant abnormal vital signs, clinically relevant laboratory abnormalities, and clinically relevant ECG findings. An AE relating to a pre-existing condition will only be recorded if there is a worsening of the pre-existing condition during study conduct with regard to nature, severity or frequency.

An adverse drug reaction is an “untoward and unintended response to an IMP related to any dose administered”.

All AEs judged by either the reporting Investigator or the Sponsor as having a reasonable causal relationship to a medicinal product qualify as adverse drug reactions. The expression of “reasonable causal relationship” means to convey in general that there are facts or arguments which suggest a causal relationship.

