8.7.1 Adverse events

All AEs will be classified by Primary System Organ Class (SOC) and Preferred Term (PT) according to the most recently available version of the MedDRA dictionary.

In summaries by SOC and PT, adverse events will be sorted within each SOC and PT in alphabetical order. In summaries by PT, AEs will be sorted within each PT in alphabetical order.

Details for imputing missing or partial start dates of adverse events are described in [REDACTED]

TEAEs are defined as any AE occurring or worsening on or after the first dose of IMP. AE summary tables will be presented for TEAEs only and will include the following:

- All TEAEs
- Related TEAEs (AE will be defined as related if causality is possibly, probably, or certain)
- TEAEs by maximum severity
- TEAEs leading to discontinuation
- Serious TEAEs
- TEAEs leading to death.

An overall summary for the categories above will be prepared by study part, treatment group and overall. A TEAE in Part 1 is defined with the event start date on/after the first dose but before [REDACTED] dosing date of IMP or on/before the last dose date of IMP if the subject discontinues before [REDACTED]. A TEAE in Part 2 is defined with the event start date on/after [REDACTED] dosing

Statistical Analysis Plan (SAP)

date but on/before the last dose date of IMP. A TEAE in Part 3 is defined with the event start date after the last dose date of IMP.

In addition, all TEAEs will be summarized by study part (Parts 1, 2, 3), SOC, PT and treatment group using frequency counts and percentages (i.e., number and percentage of subjects with an event).

Where a subject has the same adverse event, based on preferred terminology, reported multiple times in a specific study part, the subject will only be counted once at the preferred terminology level in adverse event frequency tables.

Where a subject has multiple adverse events within the same system organ class in a specific study part, the subject will only be counted once at the system organ class level in adverse event frequency tables.

When reporting adverse events by intensity, in addition to providing a summary table based on the event selection criteria detailed above, summary table will also be provided based on the most intense event - independent of relationship to study treatment.

Adverse Events of Special Interest (AESIs)

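### The partial-date rule for adverse events turns events with a known pre-dose month or year into Part 1 TEAEs when they are still present at first dose

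*SAP*

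**What the plan says.** SAP 7.2.2 has three branches for an incomplete adverse-event start date.

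- Day missing: "If the start date has month and year but day is missing, the first day of the month will be imputed".
- Day and month missing: "If the start date has year, but day and month are missing, the 1st of January will be imputed".
- Everything missing: "If the start date of an event is completely missing, then it is imputed with the first dose date".

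The first two branches each carry the same two bullets: "If this date is earlier than the first dose date, then the first dose date will be used instead", followed by "If this date is later than the stop date (possibly imputed), then the stop date will be used instead". The third branch has neither. Partial stop dates are pushed late; for a missing day, "If the stop date has month and year but day is missing, the last day of the month will be imputed".

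SAP 8.7.1 then classifies on the result: "TEAEs are defined as any AE occurring or worsening on or after the first dose of IMP". The same section uses the start date to place each TEAE in Part 1, 2 or 3.

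Protocol 12.1.1.1 covers observations recorded on the adverse-event form from an earlier period. The name of that period is blacked out, but the next sentence turns to what follows the first dose. These earlier observations "will not be considered treatment-emergent AEs (TEAEs) and will be reported separately from TEAEs". SAP 8.7.1 confirms that pre-treatment events are in the data, since it lists them.

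**The concern.** Moving a partial date to first dose is reasonable when the record leaves open whether the event began before or after dosing. The SAP rule goes further: it also moves dates whose known part already settles the matter. For an event recorded as February in a subject first dosed in March, the missing day cannot change the answer, yet the rule overwrites what was recorded.

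Safety and tolerability form the primary safety objective (Protocol 8.2), and TEAE tables by study part and treatment group are a main output for it. Events that the protocol wants reported separately would enter those tables. A second effect concerns study part. A year-only start in the dosing year goes to first dose and hence to Part 1, even if the event began in Part 2, when the placebo arm was already on tildrakizumab.

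**Working it through.** The documents state no figure on this point. The check traces the rule and then measures how far it reaches under stated assumptions.

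**Tracing the rule.** Take an illustrative first dose on 15 March 2018. *In order* means that the stop-date bullet is applied to the date left by the first-dose bullet. *Against the raw date* means that both bullets are compared with the first of the month or 1 January.

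| Recorded start | Stop | In order | Against the raw date |
|---|---|---|---|
| February 2018, day unknown | ongoing | 15 Mar 2018, Part 1 TEAE | same |
| February 2018, day unknown | 25 Mar 2018 | 15 Mar 2018, Part 1 TEAE | same |
| February 2018, day unknown | 28 Feb 2018, or February with day unknown | 28 Feb 2018, pre-treatment | 15 Mar 2018, Part 1 TEAE starting after it stopped |
| 2017 only | ongoing | 15 Mar 2018, Part 1 TEAE | same |
| 2018 only | ongoing | 15 Mar 2018, Part 1 TEAE | same |
| 2019 only | ongoing | 1 Jan 2019, Part 2 | same |

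Rows 1, 2 and 4 are the defect: the recorded month or year proves pre-dose onset, and the event still becomes a TEAE under either reading. Row 3 shows that the protection for events that ended before dosing depends on an order the SAP does not give. A completely missing start with a stop date of 28 February 2018 would be set to 15 March 2018, because that branch has no stop-date check.

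**How often a missing day leaves a provably pre-dose month.** Inputs: screening runs from Day -28 to Day 0 (Protocol contents list, 9.1.3.1). Assume that pre-dose onsets are uniform over days -28 to -1 and that first doses are uniform over a 365-day year. If first dose falls on day d of a month, max(0, 29 - d) of the 28 preceding days lie in an earlier month. Summed over d, that is 28 + 27 + ... + 1 = 406 per month. The share is 12 × 406 / (365 × 28) = 4,872 / 10,220 = 47.7%. These are the cases the rule can misclassify, and only if the event is still present at first dose. In the other 52.3% the onset shares the month of first dose, and the substitution is a defensible choice.

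**Year-only starts and study part.** Inputs: Part 1 runs to Week 24 (24 × 7 = day 168) and the last planned dose is at Week 48 (day 336). The exact dosing visit that divides Parts 1 and 2 is blacked out in SAP 8.7.1, so day 168 is an assumption.

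- Year equal to the dosing year: the date becomes first dose, so Part 1, unless the stop date is earlier.
- Year after the dosing year: the date is 1 January. Over the 365 possible first-dose days, 1 January falls in Part 1 for 167 (first dose from 18 July), in Part 2 for 169 and in Part 3 for 29.

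Take a true Part 2 onset on day o (168 to 336) with no stop date. It is sent to Part 1 if it falls in the dosing year (365 - o of the 365 dose days), or if 1 January of the next year is still in Part 1 (167 dose days). The share is (532 - o)/365. The average o is 252, so the mean share is 280/365 = 77%, assuming uniform onset and dose day.

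**Scale.** SAP 5 plans about 45 subjects per arm in each cohort: 1/45 = 2.2 percentage points per subject.

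**The case against.** The case for leaving the rule alone has several parts.

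- *It is conservative, because it counts more TEAEs.* That holds where onset is ambiguous. It does not justify overriding a recorded month or year. Real worsening would not be lost without the rule: Protocol 12.1.2 calls for a new record when severity changes, and SAP 8.7.1 counts worsening after dosing.
- *The affected events are few.* This largely stands. Start and stop dates are required for every event, and dosing visits are four weeks apart. Screening is nominally 28 days, so a prior-year start normally needs dosing in January. Protocol 12.1.1.1 records an event tied to a pre-existing condition only if it worsens.
- *It does not favour an arm.* For pre-dose onsets this stands: they precede treatment in a randomised, blinded trial and the rule is the same for both arms.
- *Safety is descriptive and every event is listed.* Also true. It limits the harm but does not correct the tables.

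A reader might infer that every event with a partial pre-dose date becomes a TEAE. Read in order, the stop-date bullet keeps events that ended before dosing out. A reader might also infer that all year-only events default to Part 1. For a year after the dosing year the date is 1 January, which can fall in any part. Nor do the documents show that the rule flatters tildrakizumab by shifting events into the placebo column. That can happen to a placebo subject's post-switch event, but Part 2 events in the tildrakizumab arm are moved to Part 1 in the same way, and no count is available for either arm.

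**Conclusion.** The point holds in a limited form. For an event that is ongoing at first dose, or ends on or after it, and whose recorded month or year is earlier than that of first dose, SAP 7.2.2 produces a Part 1 TEAE where the protocol calls for separate reporting. This follows from the text alone and does not depend on how the bullets are ordered. Two gaps sit beside it: the order of the bullets is unstated, and a completely missing start date is not checked against the stop date. Year-only starts in the dosing year are placed in Part 1 regardless of the true part.

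The effect on the TEAE tables is unknown because the number of partial dates is not given. The 47.7% and 77% describe how the rule acts on an affected date under uniform-onset assumptions; they do not estimate misclassified events in this trial. The 2.2 points is the weight of one subject, not an observed shift. The correction is worth making because the stated rule gives a wrong classification and costs little to repair. No efficacy conclusion is touched.

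**What to change.** Revise SAP 7.2.2 as follows.

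1. Use the first dose date for a partial start only when the known month and year (or the year, if the month is missing) equal those of first dose and the stop date is not before first dose.
2. If the known part is earlier than that of first dose, keep the event as pre-treatment. Worsening after dosing still counts as a TEAE.
3. Apply the stop-date check last, and in all three branches, including completely missing start dates.
4. If wanted, flag year-only events that could fall in more than one study part, in the same way in both arms.

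I would not assign ambiguous events to the part in which the subject was on tildrakizumab. That is undefined for the tildrakizumab arm, which is on drug in both parts, and it would make Part 1 classification depend on the arm.

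The cost is a few lines of derivation code and possibly a slightly lower TEAE count. A count of partial start dates by arm, reported beside the tables, would show whether the change matters. If outputs already exist under the current rule, SAP 1 provides for describing and justifying the departure in the study report.
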